7.5. Pre and Post-Intervention Measures

Participants who meet study criteria and who remain interested in participating in the 12 week intervention will undergo a baseline/ pre-intervention testing and be randomized to treatment or sham groups. The pre-intervention measures will be administered by research assistants or psychometrists who are blinded to group assignment (sham, real NIR stimulation).

[figure not shown]
Pre-intervention/baseline testing involves cognitive and mood measures, questionnaires, blood draw, and neuroimaging. The cognitive measures include tasks of executive function, recent memory, and processing speed. The mood measures include the emotion module from the NIH Toolbox and paper-pencil questionnaires. Participants will undergo brain imaging (1.5 hrs). These same measures will be given after the 12 week intervention has been completed and again at 3 months post-intervention. The exception is neuroimaging and a blood draw which are not given at the 3 month follow-up.

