8.2. Randomization and Statistical Methods

8.2a. Randomization

Participants will be independently assigned to Sham and Active groups on a 1:1 ratio. Randomization will be stratified according to age and MoCA scores so as to prevent different average ages or cognitive status scores between the treatment groups (Active, Sham). Treatment assignment will be pseudorandomized in order to have comparable distributions of age and cognitive screening scores across Sham and Treatment interventions. Procedures will be followed so that group assignments are not available to individuals administering and scoring baseline/pre-intervention and post-intervention cognitive/mood data.

8.2b. Missingness and Intent to Treat

All data will be checked for missingness, out-of-range values, and distributional form (i.e., normality, homogeneity of variance). Decisions regarding use of parametric vs. nonparametric statistics will be based on the results of those analyses. Standard summary statistics will be provided for pre- and post-stimulation. Intent to treat analysis will be used to reduce selective attrition bias; participants who are unwilling/unable to continue with intervention will be encouraged to attend the post intervention testing, if possible. Thus, statistical analyses will be performed on two data sets: 1) on all subjects who were successfully screened, randomized and able to participate in at least 1 week of the assigned intervention, regardless of study completion (intention-to-treat analysis); and 2) on subjects who were successfully screened, randomized and able to complete at least 80% of the treatment assignment.

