8.4. Methodological Limitations

Few previous human studies have conducted sham controlled trials. Thus, there is a potential impact of placebo in producing positive effects on cognition. The current study attempts to control for this. Another issue pertains to the penetrance of near infrared light through the skull. Most transcranial NIR light applied to the human cranium penetrates 1 cm into the tissue, reaching cortical tissue but not white matter or subcortical structures. As a result, the dosage reaching particular brain structures depends on a variety of factors such as cranium thickness, degree of cortical atrophy, penetrance, source of light, and duration of treatment/energy density of light.

9. Study Time Line Schedule of Activities

The Schedule of Participant Activities for this study is as follows:

- Call #1- Telephone Prescreening to review the study details, and inclusion/exclusions.

- **Informed Consent Process and Screening Visit**- Informed Consent Process begins with the participant per UF, state and federal guidelines. Once the participant has signed the informed consent, complete medical history, inclusion/exclusion criteria, concomitant medications, and cognitive and mood questionnaires will be administered (listed in section C). The screening evaluation will take up to 1.5 hours. If participant formally meets study criteria, then he or she is invited to participate in the intervention phase of the study consisting of baseline, NIR stimulation, and post-baseline testing.
- **Baseline Assessment** - This assessment involves a series of computer based measures and other questionnaires, along with a brain scan and blood draw. This cognitive and mood assessment may take up to 5 hours and may be broken up across days, if necessary. The brain imaging will take between 60-80 minutes and the blood draw approximately 30 minutes.

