All data will be checked for out-of-range values, and distributional forms (normality, homogeneity of variance). Decisions regarding parametric vs nonparametric statistics will be based on the results of those analyses. Standard summary statistics will be provided for pre, post- and follow-up time points. The intention-to-treat (ITT) principle will be applied whereby all randomized patients who complete the baseline assessment will be analyzed according to their assigned interventions. For studying the relationship between longitudinal outcomes and NIR stimulation effects, we will fit linear mixed effects models with subject specific random effects to account for the within subject correlation, using R software *lmer* package¹⁵⁸. Linear mixed model is robust against missing data if they are missing at random (MAR)¹⁵⁹. Baseline outcomes and covariates including age, sex, education, and other potential confounders (listed in Exploratory Aim 3) will be adjusted to take account for confounding effects. If multiple hypotheses are investigated simultaneously, multiple comparisons will be properly adjusted by using Benjamini-Hochberg correction¹⁶⁰. Below we describe how these statistical models fit the specific aims in this proposal.

Analyses for Aim 1: To test the hypothesis that the active NIR stimulation will result in greater pre-post intervention improvement in cognition (episodic memory, executive function) relative to the sham group, we will fit the following linear mixed model:

$$y_{ik} = \mu + \alpha_i + \beta \mathbb{I}(z_i = 1) + \sum_{l=0}^L \gamma_l x_{il} + \eta \mathbb{I}(k = 2) + \theta \mathbb{I}(z_i = 1, k = 2) + \varepsilon_{ik}, \alpha_i \sim N(0, \sigma_0^2), \varepsilon_{ik} \sim N(0, \sigma^2) \quad (1)$$

where y_{ik} is the outcome variable (e.g., ARENA score for Aim 1) for subject i and visit k ($k = 1$ for post-intervention and $k = 2$ for 3-month follow-up); μ is the intercept term; $\alpha_i \sim N(0, \sigma_0^2)$ is the random effect with variance term σ_0^2 for subject i ; z_i is the treatment indicator with $z_i = 0$ for sham group and $z_i = 1$ for active

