stimulation group, β is the post intervention treatment effect (active stimulation effect compare to sham group) and $\mathbb{I}(\cdot)$ is the indicator function which equals to 1 if the argument inside (\cdot) is true and equals 0 otherwise; x_{il} is the l^{th} covariates for subject i with $l = 0$ for baseline level (e.g. baseline ARENA for Aim 1) and $l = 1, 2, \dots, L$ for L covariates (i.e., age, sex, education...); η is the time effect of 3-month follow-up compared to post-intervention visit; θ is the interaction effect between follow-up and active stimulation; $\varepsilon_{ik} \sim N(0, \sigma^2)$ is the error term with variance σ^2 . In equation (1), β is the active stimulation effect for post-intervention, and we will perform the statistical hypothesis testing ($H_0: \beta = 0$) to provide its p-value, point estimate and confidence interval. Similarly, $\beta + \theta$ is the active stimulation effect after 3-month follow-up, where p-value, point estimate and confidence interval will be similarly obtained by testing the null hypothesis $H_0: \beta + \theta = 0$. Note that equation (1) will be applied to all measures in Aim 1 including the primary outcome (ARENA), secondary outcomes (working memory), and other exploratory outcomes (verbal fluency, mnemonic similarity, auditory verbal learning test, and Stroop color word test).

Analyses for Aim 2: To test the hypothesis that NIR stimulation will result in greater pre-post intervention improvement in neuroimaging (31P MRS for ATP and rs-fMRI for connectivity) relative to the sham group, we will fit the following linear mixed model:

$$y_{ik} = \mu + \alpha_i + \beta \mathbb{I}(z_i = 1) + \sum_{l=0}^L \gamma_l x_{il} + \varepsilon_{ik}, \alpha_i \sim N(0, \sigma_0^2), \varepsilon_{ik} \sim N(0, \sigma^2) \quad (2)$$

Equation (2) is similar to equation (1), with the adjustment of the same set of covariates, except that the equation (2) doesn't have the 3-month follow-up. β is the active stimulation effect for post-intervention, for which we will perform the statistical hypothesis testing ($H_0: \beta = 0$) to provide its p-value, point estimate and confidence interval. Note that equation (2) will be applied to all measures in Aim 2 including secondary outcomes involving ATP from 31P MRS (H2.1) and connectivity from, rs-fMRI (H2.2).

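### Protocol 8.2b gives the intention-to-treat label to a set that requires at least 1 week of intervention; the SAP's ITT set has no such condition, and the two need to be reconciled

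*Protocol*

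**What the plan says.** Protocol 8.2b names two analysis sets. The first, called intention-to-treat, takes in those who were screened, randomised and "able to participate in at least 1 week of the assigned intervention, regardless of study completion (intention-to-treat analysis"). The second takes in those "able to complete at least 80% of the treatment assignment". The same paragraph also says that "participants who are unwilling/unable to continue with intervention will be encouraged to attend the post intervention testing, if possible".

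The Protocol's other ITT statement, in 7.2 under Sample Size, Attrition, Power, and Intent to Treat, sets no minimum exposure.

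The SAP (Statistical Analysis) says that "all randomized patients who complete the baseline assessment will be analyzed according to their assigned interventions". It sets no exposure condition and does not mention the 80%-completion set.

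**The concern.** One label covers two populations. The SAP's condition, completing baseline, appears to be met before allocation: Protocol 7.5 has participants undergo "pre-intervention testing and be randomized to treatment or sham groups", in that order. The Protocol's condition, a week of assigned intervention, can be met or missed only after allocation. Excluding people on that basis gives up part of the protection of randomisation, which is the protection 8.2b says it wants from ITT.

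The people affected are those who stop in week 1 and still come back. They are among the participants 8.2b encourages to attend, yet their outcome data would be left out of the set it calls ITT. Those who stop later are kept. If week-1 exclusions differ between arms in number or kind, the comparison is biased. In addition, either set could be reported as the ITT result after the data are seen.

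**Working it through.** **1. Who separates the two sets.** In the SAP's equation (1), the outcome visits are post-intervention and 3-month follow-up, and the baseline outcome is a covariate ("for baseline level (e.g. baseline ARENA for Aim 1"). Equation (2) has only the post-intervention visit. A week-1 leaver who never returns therefore adds nothing under either set. The sets differ for leavers who return.

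**2. The planning figure.** Inputs from the SAP: smallest d = 0.48 (prefrontal ATP), alpha 5%, power 80%, 15% attrition. The Protocol gives a two-tailed test. A two-sample t-test needs 70 per arm, and 70/0.85 rounds up to 83, against the stated 84. Power at 84 × 0.85 = 71.4 per arm is 0.813. The choice of set does not enter this calculation.

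**3. How many people (assumed rates).** Neither document gives a week-1 exit rate. At 2%, 5% or 10% of 168, about 3, 8 or 17 randomised participants would fall outside the Protocol set.

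**4. Bias in the 1-week set when every excluded leaver returns.** Let fA and fS be the shares excluded in the active and sham arms. Let g be the leavers' deficit relative to those who stay, in residual SD, after the SAP's covariate adjustment. Then

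bias = (fA − fS) × g.

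With 71 per arm before exclusions and no true effect, the noncentrality is bias divided by √(1/nA + 1/nS):

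| Assumption | Excluded per arm | Bias | Noncentrality | False positives at nominal 5% |
|---|---|---|---|---|
| 8% v 2%, g = 0.5 | about 6 v 1 | 0.06 × 0.5 = 0.03 SD | 0.03/0.172 = 0.17 | 5.3% |
| 10% v 0%, g = 1.0 | about 7 v 0 | 0.10 × 1.0 = 0.10 SD | 0.10/0.172 = 0.58 | 8.9% |
| 5% v 5%, g = 1.0 | about 4 v 4 | 0 | 0 | 5% |

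A simulation of 20,000 runs (ANCOVA on baseline, assumed slope 0.6) gave 5.3%, 8.9% and 4.8%. The SAP set, with all leavers returning, gave no bias and 5.1%, 5.2% and 4.9%. As shares of the ARENA planning effect (d = 1.06), the biases are 0.03/1.06 = 2.8% and 0.10/1.06 = 9.4%.

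**5. Bias left in the SAP set when only a fraction r return.** Leavers then make up fr/(1 − f + fr) of those observed, so each arm's mean is shifted by g × [f − fr/(1 − f + fr)]. For 10% v 0% with g = 1.0:

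| Return rate | Bias in SAP set | False positives |
|---|---|---|
| All | 0 | 5.0% |
| Half | 0.10 − 0.05/0.95 = 0.047 SD | 5.9% |
| A quarter | 0.10 − 0.025/0.925 = 0.073 SD | 7.1% |
| None | 0.10 SD | 8.9% |

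In the last row the two sets are the same.

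**6. Dilution from keeping leavers.** Assume returning leavers get no benefit and are 5% or 10% of each arm, with d = 0.48 and 15% attrition.

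- *Leavers additional to the 15% (71 per arm).* ITT effect 0.48 × 0.95 = 0.456 or 0.48 × 0.90 = 0.432, power 0.770 or 0.725. The 1-week set (67.5 or 63.9 per arm) has 0.790 or 0.768.
- *Leavers part of the 15%.* ITT has 75.6 or 79.8 per arm and d = 0.453 or 0.429, power 0.791 or 0.769. The 1-week set has 0.813.

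The loss is about 2 to 4 points. At the Protocol's 30% attrition it is about 2 to 6 points. ARENA power stays above 0.99 in every case.

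**The case against.** The SAP already gives the standard definition, and two of the three ITT statements in the documents lack the 1-week condition. On this view one clause needs harmonising and little else.

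Several features make unequal week-1 exits unlikely. Sham devices look identical and outcome testers are blinded (Protocol 7.6.3). The light is described as painless (section 13). Documentaries limit talk with the session staff, who do know the assignment (7.6.2 and 7.6.3). The extreme case needs about 10% of one arm and nobody in the other to leave in the first week, in a trial that plans for 15% attrition overall. The $350 payment tied to completing the intervention, post-MRI and follow-up (7.8) also suggests that few week-1 leavers would return, and then changing the set removes little bias. The SAP's adjustment ("Baseline outcomes and covariates including age, sex, education, and other potential confounders") reduces it further.

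Most of this stands, and it limits the size of the problem. It does not remove the conflict: the Protocol still gives the ITT label to a set conditioned on treatment received.

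A reader might infer three stronger things that the documents do not support:

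- *That the primary comparison is materially biased.* No exit rate is given, and equal exclusion of similar people gives no bias.
- *That the SAP set is free of bias.* This holds only if all the leavers return.
- *That no rule of precedence exists.* Title and signature pages are not in the supplied text, so one can say only that the text available contains none.

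**Conclusion.** The inconsistency is real. Protocol 8.2b describes a modified ITT set under the ITT label, and the SAP describes a different set under the same label.

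The numerical consequence is probably small: 0.03 SD and 5.3% false positives under a moderate assumed imbalance, 0.10 SD and 8.9% under an extreme one. Both figures assume that all excluded leavers return, and both rest on exit rates and deficits that the documents do not give. The case for acting rests mainly on fixing one primary population before the data are seen. This is a minor point of wording that should be corrected because it concerns the primary analysis set and costs almost nothing.

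**What to change.** Delete the 1-week condition from the ITT definition in Protocol 8.2b, and put the same text in the Protocol and the SAP:

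> The primary analysis set is all randomised participants with a baseline value of the outcome being analysed, analysed as assigned (intention-to-treat), whatever intervention they received; those with at least one post-baseline value contribute to the model. The set with at least 1 week of assigned intervention (modified ITT) and the set completing at least 80% of the treatment assignment (per protocol) are sensitivity analyses.

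Requiring the baseline value of the outcome matches the baseline covariate in equations (1) and (2), which do not change. Treating the 80% set as a sensitivity analysis is a proposal, since 8.2b does not rank its two sets. The wording does not settle what happens when another adjustment covariate is missing; the SAP would need a separate line for that.

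The cost is one sentence in each document, with no new data, visits or participants. The downside is the slight dilution shown above, about 2 to 4 points of power for the smallest planning effect under the stated assumptions, with no practical loss for ARENA.

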8.3. Statistical Analyses

For hypotheses associated with Aims 1 (cognitive) and 2 (imaging), we plan to conduct linear mixed effects models and other potential analyses. For Aim 3, we are interested in predictors of treatment responses and will explore a variety of potential mediators and/or moderators including APOE-4 carrier status, vascular comorbidities (including white matter burden), mood/emotion, processing speed, and demographic variables. To examine confounders, we will directly adjust these variables as covariates in a linear mixed model. Additional analyses will be conducted as appropriate.

8.4. Methodological Limitations

Few previous human studies have conducted sham controlled trials. Thus, there is a potential impact of placebo in producing positive effects on cognition. The current study attempts to control for this. Another issue pertains to the penetrance of near infrared light through the skull. Most transcranial NIR light applied to the human cranium penetrates 1 cm into the tissue, reaching cortical tissue but not white matter or subcortical structures. As a result, the dosage reaching particular brain structures depends on a variety of factors such as cranium thickness, degree of cortical atrophy, penetrance, source of light, and duration of treatment/energy density of light.

9. Study Time Line Schedule of Activities

The Schedule of Participant Activities for this study is as follows:

- Call #1- Telephone Prescreening to review the study details, and inclusion/exclusions.

- **Informed Consent Process and Screening Visit**- Informed Consent Process begins with the participant per UF, state and federal guidelines. Once the participant has signed the informed consent, complete medical history, inclusion/exclusion criteria, concomitant medications, and cognitive and mood questionnaires will be administered (listed in section C). The screening evaluation will take up to 1.5 hours. If participant formally meets study criteria, then he or she is invited to participate in the intervention phase of the study consisting of baseline, NIR stimulation, and post-baseline testing.
- **Baseline Assessment** - This assessment involves a series of computer based measures and other questionnaires, along with a brain scan and blood draw. This cognitive and mood assessment may take up to 5 hours and may be broken up across days, if necessary. The brain imaging will take between 60-80 minutes and the blood draw approximately 30 minutes.
- **NIR Intervention (16 sessions over twelve weeks)**- After completing baseline testing, participants will undergo 12 weeks of intervention. This includes 16 'in lab' sessions and daily at home intranasal sessions. The laboratory sessions will be scheduled at the baseline visit to ensure availability of the participant. The transcranial treatment will be applied over the head and is detailed in section 7.6. During each treatment visit, participants will fill out mood questionnaires such the POMS. During this 12 week period, participants will also complete daily journal indicating the time and location of their at home intranasal stimulation.
- **Post-Treatment Visit**- Following the final day of stimulation, the participant will be scheduled for a post-testing assessment of cognition, emotion, and neuroimaging, identical to the baseline visit. Participants will also fill out other questionnaires such as the adverse events and placebo control questionnaires and will be scheduled for a final blood draw.
- **3 Month Follow-up Visit** - Participants will receive final assessment of cognitive and emotion measures. They will not undergo MRI or a blood draw.

10. IRB Plan

The proposed study involves parallel data collection at two sites, the University of Florida and the University of Arizona. We plan to use a single IRB plan in compliance with NIH policy. Both the University of Florida and the University of Arizona are members of the SMART IRB, a master common reciprocal Institutional Review Board Authorization Agreement, which outlines standard operating procedures and guidelines for establishing reliant review of multi-site research.

We plan to establish the University of Florida as the IRB of record (Central IRB), whereas the University of Arizona will be the Relying IRB. As such, the UF IRB will provide ethical review for both UF and UA, whereas UA will retain responsibility for local institutional reviews (i.e., training, conflict of interest, HPPA privacy, biosafety, etc.). Additionally, UF will be the privacy board, and the relying IRB will be required to inform UF if there are any state HIPAA regulations in addition to Federal. [name] (MPI), as the contact PI, will be responsible for the communication and overall conduct of the study and regulatory compliance and will submit regulatory IRB submissions on behalf of UF and the UA site. [name], MPI at the University of Arizona, will provide [name] necessary information according to UF-IRB policies and procedures so that UF (Central IRB) can conduct an IRB review.

11. Data Safety Monitoring Plan

This project is very low risk to participants. The research team will follow procedures for data safety and monitoring per IRB guidelines. The research team will closely monitor participants for any potential adverse events. During the intervention phases, participants will complete adverse event questionnaires to assess for negative effects on safety of participants. These will be reviewed after every intervention session and at the follow-up evaluations. As this intervention involves an infrared lamp that is considered a non-significant risk, we do not anticipate adverse events or side effects. However, should a participant experience an adverse event of sufficient concern at any point during the intervention or at follow-up, we will report to the IRB as directed and to the Safety monitors at each site (i.e., [name] at the University of Florida and [name] at the University of Arizona) who will complete Event Notification and Evaluation forms. The MPI's and Safety Officers will meet monthly via phone or other media to discuss any adverse events, should they occur. If there are no reported adverse events, then an email notification will be sent that month in lieu of a meeting.

We plan to have a **Data Safety Monitoring Board (DSMB)** who will consist of experts in cognitive interventions, clinical trials and neuroimaging. The committee will meet every six months via telephone, Skype, Zoom, or other format. Initially, the DSMB will advise NIH staff and MPI's on design and protocol changes, the analysis plan, and planned publications. The DSMB will monitor site performance through semi-annual reports from the research team.

12. Data Management Plan

Data will be kept in a password protected encrypted database which can only be accessed by the investigators and staff. All surveys and assessments will be under the direction of the Investigators who will supervise Research Assistants. Recruitment, screening, and project implementation will be coordinated by the Investigators and/or research staff. The data management group, supported by the IT department of the College of Public Health and Health Professions, will manage the database, monitor subject recruitment and distribute monthly enrollment reports, and produce reports summarizing the status of data acquisition, the baseline characteristics and the blinded primary variables. The database mentioned above is the storage place for all participants who call and wish to be pre-screened for the study. In many instances, the prospective participant no longer wants to enroll in the study, once they learn of the time commitment and details involved in participating.

Data Sharing with Collaborating Site: With permission of participants, de-identified data will be shared between the University of Florida and the collaborating site, the University of Arizona. De-identified questionnaire, cognitive, mood, and other data will be stored via the secured infrastructure of the University of Florida REDCap System. De-identified raw neuroimaging data will be transferred using Secure File Transfer Protocol (SFTP) onto UF Dropbox servers.

13. Possible Discomforts and Risks

The risks are minimal for individuals who participate in this study. Light is applied using light emitting diodes, which do not present as a serious ocular hazard. Near infrared light is non-thermal, painless, and is designated as a non-significant risk. It is estimated that approximately 6 J/cm^2 is expected to reach the cortex with each daily treatment. At this energy level, the MedX system and/or the

Vielight intranasal system do not cause tissue damage or physical damage. Both the Medx and Vielight systems are commercially available to the public.

There are five types of potential risks for participants in this study.

First, the completion of various screening and cognitive probes could potentially become boring or tiresome. To minimize fatigue associated with completion of screening and baseline tasks, participants will be given frequent breaks and the opportunity to rest.

Second, there is potential risk of loss of confidentiality. This will be minimized through assigning all data collection instruments a unique code without individual identifying information. A separate file linking the participant to their ID code will be stored separately in a password protected server/database. All HIPAA regulations pertaining to protection of participants and eliminating identification will be followed.

Third is discomfort associated with undergoing an MRI. Because the MRI scanner has a strong magnet, individuals with metal implanted in their body cannot participate. The scanner produces a loud hammering noise, which has produced hearing loss in a very small number of participants. All participants are provided with ear protection while in the scanner. There is not much room in the scanner and it can be uncomfortable to remain still for the scan. Individuals with known claustrophobia will be excluded from participating.

Fourth, it is also possible that incidental findings may emerge on the MRI. In this situation, the participant will be informed and recommendation/referrals will be made with the participant's permission. This could include provision of information to the participant's primary care physician and/or referral to another health care professional for follow-up.

Fifth, there may be minor discomfort associated with having a blood draw taken. This is similar to what occurs when an individual has a blood draw as part of a standard clinical workup.

It is possible that there are unknown risks for participating in this study. Individuals will be asked about side effects at each visit and encouraged to share information about subjective changes.

14. Guidelines and Risks in Relation to the COVID-19 Crisis

Our study requires visits by older adults who may be at increased health risks related to COVID-19. We are addressing these risks in several ways by following guidelines provided by the State of Florida, the County, University of Florida, and the CDC. We will also follow guidelines put forth by the AMRIS facility for completion of MRI scans.

General Approach:

The research staff will check their own temperature daily upon entry into the laboratory. All will wear masks, practice social distancing, and wash hands or use sanitizer multiple times throughout the day. The only time a mask is not needed is when the individual works alone in an isolated office space. If an individual has a fever, or feels ill, they will leave the building immediately and return home. They will make arrangements to participate in the UF Health Test and Trace Program and will not return to the laboratory until cleared to do so.

The laboratory will be cleaned at least daily. Moreover, door-knobs, light switches, and touched surfaces (table tops, chairs, keyboards, mice, etc.) will be disinfected regularly, including before and after each participant is tested.

Study-Related Interactions with Participants

Upon entry into the Fixel Institute where our laboratory is located, all participants have their temperature screened by Fixel staff. Again, if a participant shows evidence of a temperature they will leave the building, return home, and are encouraged to seek guidance from their PCP.

Gloves and masks will be worn when a study coordinator interacts with a study patient. Participants will be expected to bring and wear a mask when attending a lab visit. If they do not bring one, participants will be given a mask to use and keep.

The offices that will be used for cognitive testing allow at least 6 feet separation between the participant and study coordinator. For the intervention, we are required to apply six light emitting diodes (LED's) on the scalp of the participant. As is standard practice, the LED's are cleaned before and after each use with sanitizer. During application of the diodes to the head (for NIR stimulation), the study coordinator will wear gloves. Again, as is standard practice, each participant will have their own unique 'net' for holding the diodes in place. The diodes will be sanitized with alcohol or other appropriate disinfectants after each intervention session. Finally, each participant has their own 'intranasal' stimulator that is used only by them throughout the study, both at home and during lab visits. These are cleaned using sanitizers.

If other lab personnel are in the lab on the day the patient is there, their office doors will be closed during the patient visit. We will use a staggered schedule for participant visits to avoid overlapping entry and exit into and out of the testing suite.

After Visit Procedures

After the study visit, the laboratory will be cleaned. This includes disinfecting door-knobs, light switches, and touched surfaces (table tops, door handles, keyboards, mice, pens, etc.) The diodes used for the intervention will be sanitized using recommended disinfectants.

Optional Telehealth Screening: We will offer participants the option to undergo the screening evaluation via telehealth. This option will depend on whether they have a computer or IPAD that can be safely and securely connected to the internet. If so, we will send the participant and their informant two copies each of the consent form. We will set up a time to review the consent forms via telephone. If participant continues to be interested, they will return signed copies of the consent forms in a pre-addressed stamped envelope. Once we receive the signed consent forms, we will set up the telehealth screening. This will be done via a UF zoom platform that is HPPA compliant, and identical in format to what we use in our clinical visits with patients at UF Health. With one exception, the majority of the relevant screening measures can be administered via telehealth. The exception is the Trailmaking Test, which will be given during the baseline visit instead of the screening visit.

15. Possible Benefits

